5.1. Inclusion Criteria

A subject will be eligible for inclusion in this study only if all of the following criteria apply:

[1] AGE

- Between 18 and 55 years of age inclusive, at the time of signing the informed consent.

[2] TYPE OF SUBJECT

- Healthy as determined by the investigator or medically qualified designee based on a medical evaluation including medical history, physical examination, laboratory tests and cardiac monitoring.
- A subject with a clinical abnormality or laboratory parameter(s) which is/are not specifically listed in the inclusion or exclusion criteria, outside the reference range for the population being studied, may be included only if the investigator in consultation with the Medical Monitor, if required, agree and document that the finding is unlikely to introduce additional risk factors and will not interfere with the study procedures.

[3] WEIGHT

- Body weight \geq 60 kg and body mass index (BMI) within the range 19 to 29.9 kg/m² inclusive.

[4] SEX

- Male
- Female subjects of non-child bearing potential are eligible to participate. Non-child bearing potential is defined as:
 - Pre-menopausal females with one of the following:
 - Documented tubal ligation
 - Documented hysteroscopic tubal occlusion procedure with follow-up confirmation of bilateral tubal occlusion or documented bilateral salpingectomy
 - Hysterectomy
 - Documented Bilateral Oophorectomy
 - Postmenopausal defined as 12 months of spontaneous amenorrhea. Postmenopausal status will be confirmed by a simultaneous FSH and estradiol levels test.
- Male subjects with female partners of child bearing potential must comply with the following contraception requirements from the time of first dose of study medication until **90 days** after the last dose of study treatment (i.e. one sperm cycle).
 - Vasectomy with documentation of azoospermia.
 - Male condom plus partner use of one of the contraceptive options below:
 - Contraceptive subdermal implant
 - Intrauterine device or intrauterine system
 - Highly effective oral contraceptive, either combined or progestogen alone (provided it's associated with inhibition of ovulation)
 - Injectable progestogen
 - Contraceptive vaginal ring
 - Percutaneous contraceptive patches
- These allowed methods of contraception are only effective when used consistently, correctly and in accordance with the product label. The investigator is responsible for ensuring that subjects understand how to properly use these methods of contraception ([Appendix 3](#)).

[5] INFORMED CONSENT

- The subject is able to understand and comply with protocol requirements, instructions and protocol-stated restrictions.

5.2. Exclusion Criteria

A subject will not be eligible for inclusion in this study if any of the following criteria apply:

[1] CONCURRENT CONDITIONS/MEDICAL HISTORY (INCLUDES LIVER FUNCTION AND QTc INTERVAL)

- Alanine aminotransferase (ALT) and bilirubin $>1.5 \times$ upper limit of normal (ULN) (isolated bilirubin $>1.5 \times$ ULN may be acceptable, after consultation with the GSK Medical Monitor, if bilirubin is fractionated and direct bilirubin $<35\%$).
- Current or chronic history of liver disease, or known hepatic or biliary abnormalities (with the exception of Gilbert's syndrome or asymptomatic gallstones).
- QTcF >450 msec.
- Presence of moderate or severe valve disorder or any other clinically significant abnormality.
- Subjects with a history of photosensitivity.
- Females of non-childbearing potential who are susceptible to heavy periods or vaginal bleeding or spotting.
- Pregnant females. A human chorionic gonadotrophin (hCG) test will be performed on Day-1 of each treatment (dosing) period in Part A and Part B for women for whom post-menopausal status has not been confirmed by follicle stimulating hormone (FSH)/estradiol testing. No pregnancy tests will be required for female subjects confirmed as post-menopausal by FSH/estradiol testing.
- Lactating females.

[2] CONCOMITANT MEDICATIONS

- Use of prescription or non-prescription drugs, including high-dose vitamins, herbal and dietary supplements (including St John's Wort) within 7 days (or 14 days if the drug is a potential enzyme inducer) or 5 half-lives (whichever is longer) prior to the first dose of study medication, unless in the opinion of the Investigator and sponsor the medication will not interfere with the study procedures or compromise subject safety. Paracetamol for mild analgesia will be permitted.

[3] RELEVANT HABITS

 • Breath carbon monoxide test indicative of smoking or history of current use of tobacco- or nicotine-containing products. • Current regular alcohol consumption defined as: 
 • An average weekly intake of >21 units for males or >14 units for females. One unit is equivalent to 8 g of alcohol: a half-pint (~240 ml) of beer, 1 glass (125 ml) of wine or 1 (25 ml) measure of spirits. • Subjects must not sunbathe or use a tanning device (e.g. sunbed or solarium) whilst taking the study medication and until at least 2 weeks after their last dose. Subjects are to be advised that they should wear protective clothing (e.g. sun hat, long sleeves) and use a broad spectrum UVA/UVB sunscreen (SPF ≥ 30) when outdoors.
[4] CONTRAINDICATIONS

 • History of sensitivity to heparin or heparin-induced thrombocytopenia. • History of sensitivity to any of the study medications, or components thereof or a history of drug or other allergy that, in the opinion of the investigator or Medical Monitor, contraindicates their participation.
[5] DIAGNOSTIC ASSESSMENTS AND OTHER CRITERIA

 • Presence of hepatitis B surface antigen (HBsAg), positive hepatitis C antibody test result at screening or within 3 months prior to first dose of study treatment. • A positive test for HIV antibody. • A positive pre-study drug/alcohol screen. • The subject has participated in a clinical trial and has received an investigational product within the following time period prior to the first dosing day in the current study: 3 months, 5 half-lives or twice the duration of the biological effect of the investigational product (whichever is longer). • Exposure to more than four new chemical entities within 12 months prior to the first dosing day.

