5. SELECTION OF STUDY POPULATION AND WITHDRAWAL CRITERIA

Consent for screening evaluations may be obtained using the information and consent form for the HMR healthy volunteer panel, which has been approved by the Health Research Authority's Generic Document Review Committee. The trial-specific information and consent form will be signed by the subject either before any study-specific screening evaluation or after the investigator confirms the eligibility of the subject for the trial and before the subject is randomised to receive the first administration of study drug.

Specific information regarding warnings, precautions, contraindications, adverse events, and other pertinent information on the GSK investigational product that may impact subject eligibility is provided in the GSK3036656 Investigator's Brochure [GlaxoSmithKline Document Number [2016N305393_01](#)].

Deviations from inclusion and exclusion criteria are not allowed because they can potentially jeopardize the scientific integrity of the study, regulatory acceptability or subject safety. Therefore, adherence to the criteria as specified in the protocol is essential.

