5.4.1.1. Study Treatment Restart or Rechallenge

Study treatment restart or rechallenge after liver chemistry stopping criteria are met by any subject participating in this study is not allowed.

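### The liver exclusion in Protocol 5.2 is internally inconsistent: read literally it needs ALT and bilirubin both raised, but its bracket works only if one raised value excludes by default

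*Protocol*

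**What the plan says.** The exclusion list in Protocol 5.2 opens with "A subject will not be eligible for inclusion in this study if any of the following criteria apply", so each bullet excludes on its own and the wording inside a bullet decides what that bullet covers.

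The liver chemistry bullet reads "Alanine aminotransferase (ALT) and bilirubin $>1.5 \times$ upper limit of normal (ULN"). Its bracket adds that "isolated bilirubin $>1.5 \times$ ULN may be acceptable, after consultation with the GSK Medical Monitor, if bilirubin is fractionated and direct bilirubin $<35"%.

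The next bullet excludes "Current or chronic history of liver disease, or known hepatic or biliary abnormalities", apart from Gilbert's syndrome and asymptomatic gallstones. It gives no laboratory threshold.

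Protocol 5.1 [2] requires the subject to be "Healthy as determined by the investigator or medically qualified designee based on a medical evaluation", and that evaluation includes laboratory tests. A second bullet there lets the investigator, with the Medical Monitor if required, agree and document an out-of-range value. It applies only to an abnormality or parameter "which is/are not specifically listed in the inclusion or exclusion criteria".

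The introduction to Protocol section 5 states: "Deviations from inclusion and exclusion criteria are not allowed".

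On treatment, Appendix 4 sets the liver stop at ALT of at least 3 x ULN. This is an absolute limit, not one relative to baseline. Section 5.4.1.1 adds: "Study treatment restart or rechallenge after liver chemistry stopping criteria are met by any subject participating in this study is not allowed".

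**The concern.** The two halves of one eligibility bullet cannot both be taken at face value. The opening clause, read literally, needs two raised values. The bracket carves out an exception for one. Staff told that the criteria admit no deviations should not have to choose which half governs.

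The practical stake is isolated raised ALT. If the opening clause is applied as written, the protocol has no numeric entry limit for ALT alone, although ALT is the analyte behind the liver stop. A volunteer who enters with raised ALT has less room before a permanent discontinuation, and the event could be taken for a drug effect in a dose group of 6 or 8 active subjects. In Part A the exposure to this is longer: footnote 1 of the Time and Events table limits eligibility checks on Day -1 to the first period, while a subject may go through up to four periods.

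**Working it through.** **Step 1. The bullet under each reading.** No figure in the plan needs reproducing; the check is a truth table. 'Raised' means above 1.5 x ULN.

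| ALT | Bilirubin | Literal 'and' | Reading implied by the bracket |
|---|---|---|---|
| raised | raised | excluded | excluded |
| raised | not raised | not excluded by this bullet | excluded (inferred) |
| not raised | raised | not excluded, so the bracket has nothing to except | excluded unless the Medical Monitor is consulted and fractionated direct bilirubin is below 35% |
| not raised | not raised | not excluded | not excluded |

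The readings differ in two cells: ALT raised alone, and bilirubin raised alone without the exception being met. The bracket directly shows only that raised bilirubin alone excludes by default. For ALT alone this is an inference: the two analytes share one threshold, and only bilirubin is given an exception.

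**Step 2. Other places that could stop a volunteer with isolated raised ALT.**

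| Place | Numeric ALT limit? | Basis |
|---|---|---|
| 5.1 [2], first bullet (healthy) | No | Investigator's evaluation, including laboratory tests |
| 5.1 [2], second bullet (out-of-range values) | No | Documented agreement, but only for what the criteria do not list; whether isolated ALT counts as listed is unclear |
| 5.2 [1], liver history or known abnormality | No | History or known finding |
| 5.2 [1], valve bullet, which ends with a general reference to clinically significant abnormality | No | Clinical judgement |

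None sets an ALT number.

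**Step 3. Distance from entry to the stopping limit.** Inputs: entry threshold 1.5 x ULN (Protocol 5.2); stopping limit 3 x ULN (Appendix 4). Required relative rise = 3.0 / entry value - 1. Entry values above 1.5 are illustrative, since the documents give no distribution of screening ALT.

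| ALT at entry (x ULN) | 3.0 / entry | Rise needed |
|---|---|---|
| 1.5 | 2.00 | 100% |
| 2.0 | 1.50 | 50% |
| 2.5 | 1.20 | 20% |

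An entrant at 2 x ULN or above would also already meet the SAP 10.7.1 clinical concern range for ALT before the first dose.

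**Step 4. Weight of one subject.** One such subject on active treatment is 1/6 = 17% of the active subjects in a Part A period, or 1/8 = 12.5% in a Part B cohort. These are group-size fractions, not estimates of how often it would occur.

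**The case against.** The best defence is that 'and' is a list: each of the two values above 1.5 x ULN excludes. The bracket points that way, and the protocol appears to use 'and' like this elsewhere. The risk table in 4.6.1 joins the neutrophil and lymphocyte withdrawal limits with 'and', while 5.4.3 sets them out as separate bullets. Many sites would probably read the liver bullet as a list. This stands as a likely reading, but it has to be inferred against the literal words.

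Several stronger readings are tempting, and the documents do not support them:

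- **That a site would accept such a volunteer.** Not being excluded by one bullet is not acceptance. The investigator must still find the subject healthy, and known hepatic abnormality excludes. The supportable word is 'could'.
- **That the rule controls bilirubin more tightly than ALT.** This reads the ALT half literally and the bilirubin half through the bracket. Under the literal reading throughout, neither isolated elevation is excluded.
- **That the out-of-range rule in 5.1 [2] certainly cannot apply because ALT is listed.** If only the combined elevation is listed, an isolated raised ALT is arguably unlisted and the documentation step could apply. The text does not settle this.
- **That one subject would halt escalation.** Criterion 1 in 5.5 needs a substantial excess over placebo and a team judgement. Chemistry is measured before dosing and the SAP tabulates and lists change from baseline, so a pre-existing elevation would be visible.

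It is also true that the plan gives no frequency for isolated raised ALT among volunteers, so the expected number affected cannot be stated.

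**Conclusion.** The inconsistency is real and lies within one bullet: taken literally, the opening clause leaves the bracket with no function. Under that reading, the protocol sets no numeric ALT limit at entry, and protection rests mainly on investigator judgement. The consequence is a possible entry close to the stopping limit: a 20% rise from the illustrative 2.5 x ULN, against 100% from 1.5 x ULN. It depends on a site reading the clause literally and on the judgement criteria not stopping the volunteer.

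This is a safety-relevant wording defect in an operative eligibility rule of a first-in-human study with an absolute ALT stop and no rechallenge. It does not bear on the sample size, which had no statistical basis (Protocol 10.2), or on error rates, since no hypothesis is tested. It should be corrected, but it is not evidence that subjects with liver abnormality would in fact be enrolled.

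**What to change.** Reconcile the two halves of the liver chemistry bullet in Protocol 5.2 [1] so that it says explicitly whether ALT alone above 1.5 x ULN excludes, and whether bilirubin alone above 1.5 x ULN excludes. Replacing 'and' with 'or' and keeping the isolated-bilirubin bracket is the wording consistent with that bracket, and it introduces no new threshold. The sponsor should confirm which rule was intended.

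The change is one clause. The downside is possibly a few more screen failures. No analysis, endpoint or sample size needs to change.

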5.3. Screening/Baseline/Run-in Failures

Screen failures are defined as subjects who consent to participate in the clinical trial but are never subsequently randomized. In order to ensure transparent reporting of screen failure subjects, meet the Consolidated Standards of Reporting Trials (CONSORT) publishing requirements, and respond to queries from Regulatory authorities, a minimal set of screen failure information is required including Demography, Screen Failure details, Eligibility Criteria, and any Serious Adverse Events.

5.4. Individual Withdrawal/Stopping Criteria

The following actions must be taken in relation to a subject who fails to attend the clinic for a required study visit:

[figure not shown]
- The site must attempt to contact the subject and re-schedule the missed visit as soon as possible.
- The site must counsel the subject on the importance of maintaining the assigned visit schedule and ascertain whether or not the subject wishes to and/or should continue in the study.
- In cases where the subject is deemed ‘lost to follow up’, the investigator or designee must make every effort to regain contact with the subject (where possible, 3 telephone calls and if necessary a certified letter to the subject’s last known mailing address or local equivalent methods). These contact attempts should be documented in the subject’s medical record.
- Should the subject continue to be unreachable, only then will he/she be considered to have withdrawn from the study with a primary reason of “Lost to Follow-up”.

A subject may withdraw from study treatment at any time at his/her own request, or may be withdrawn at any time at the discretion of the investigator for safety, behavioural or administrative reasons. If a subject withdraws from the study, he/she may request destruction of any samples taken, and the investigator must document this in the site study records.

5.4.1. Liver Chemistry Stopping Criteria

Study treatment will be discontinued **for a subject** if liver chemistry stopping criteria are met:

Phase I Liver Chemistry Stopping Criteria – Liver Stopping Event Algorithm

Liver Safety Required Actions and Follow up Assessments Section can be found in **Appendix 4**.

5.4.1.1. Study Treatment Restart or Rechallenge

Study treatment restart or rechallenge after liver chemistry stopping criteria are met by any subject participating in this study is not allowed.

5.4.2. QTc Stopping Criteria

A subject that meets either bulleted criterion below will be withdrawn from the study.

- QTcF >500 msec,
- Change from baseline: increase in QTcF >60 msec

Withdrawal of subjects is to be based on an average QTcF value of triplicate ECGs. If an ECG demonstrates a prolonged QT interval, obtain two more ECGs over a brief period of time and then use the averaged QTcF values of the three ECGs to determine whether the subject should be discontinued from the study.

5.4.3. Haematology Stopping Criteria

Study treatment will be discontinued for a subject if the following haematology stopping criteria are met and subjects should be followed up until values are not clinically significant.

- A reduction in haemoglobin to below 110 g/L in males and below 100 g/L in females
- A reduction in neutrophil count to below 1000/mm³ (1.0x10⁹/L)
- A reduction in lymphocyte count to below 500/mm³ (0.5x10⁹/L)

5.4.4. Vital Signs Stopping Criteria

Study treatment will be discontinued for a subject if the following vital signs stopping criteria are met:

- Clinically significant and sustained increase in resting heart rate (for example, >120 beats/minute for more than 2 hours)
- Clinically significant and sustained change in blood pressure (for example, systolic blood pressure >150 mm Hg or <85 mm Hg for more than 2 hours, or diastolic blood pressure >95 mm Hg for more than 2 hours)

5.4.5. Other Dose Adjustment/Stopping Safety Criteria

For an individual study participant, stopping criteria include, but are not limited to:

- Severe signs or symptoms, or significant changes in any of the safety assessments that put the safety of the individual at risk (e.g. ECG, vital signs,

laboratory tests etc), as judged by the Principal Investigator, in consultation with the Medical Monitor if necessary.

Any unacceptable adverse event that is thought to be related to the investigational product and any general safety finding that, in the opinion of the Investigator, gives cause for concern may result in the withdrawal of subject(s) and/or the study being paused or terminated and/or a dose adjustment.

5.5. Dose Escalation Stopping Criteria

Dose escalation in Part A or Part B will be stopped if any of the following occurs in a group/cohort:

1. There is substantially increased incidence and/or severity of clinically significant adverse events or withdrawals possibly related to GSK3036656 in the active treatment subgroup at the last dose level administered as compared to the placebo subgroup. The GSK Study Team in conjunction with the study investigator will determine the significance of the adverse events or withdrawals and make a decision about whether stopping further dose escalation is necessary.
2. At least one subject has a plasma AUC (0-24) higher than 4.9 µg.h/mL or a plasma Cmax higher than 0.443 µg/mL on any day.
3. For Part A, no meaningful increase in exposure is observed with increase in dose (i.e., a plateau in exposures is reached).

Note: If dose escalation is stopped due to reasons 1 or 2 above occurring at the last dose, dosing at a lower level (e.g., an intermediate level between the last dose and a previous dose where dose escalation stopping criteria were not met) could be allowed. The GSK Study Team in conjunction with the study investigator will decide whether dosing at such level could be done and will select the dose to be administered.

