4.5. Dose Justification

Dose selection of GSK3036656 for this FTIH study was based on no observed adverse effect level (NOAEL) data, predicted pharmacokinetics for humans using the pharmacokinetic data from various preclinical species, and a targeted therapeutic exposure based on efficacy data from a murine model of chronic lung infection. GSK3036656 PK parameters and exposure values were converted from whole blood values to plasma values when necessary. GSK3036656 suppresses protein synthesis in *Mycobacterium tuberculosis* by inhibiting the enzyme Leucyl t-RNA synthetase which is not a human target; thus, the minimum anticipated biological effect level (MABEL) in humans for GSK3036656 could not be determined.

The *in vivo* PK parameters obtained in preclinical species (CD-1 mouse, SD rat, and beagle dog) after 1 mg/kg intravenous administration and the *in vitro* parameters (intrinsic Cl from microsomes and hepatocytes, plasma protein binding, and blood to plasma ratio) were used for calculations. The GlaxoSmithKline software package PK Predictor Pro (GUI v1.1.45 Calculation Engine v1.4.4) was used for IVIVE, LBF, GFR and allometric scaling and the CloePK software (Cyprotex) for the physiologically based pharmacokinetic (PBPK) modelling.

Predicted human clearance values ranged from approximately 1.1 (allometric scaling with MLP) to 7.2 (PBPK) mL/min/kg while predicted volume of distribution ranged from 3.5 (PBPK) to 4.5 (simple allometry) L/kg. Preclinically, oral bioavailability ranged from approximately 60% to greater than 100%.

The NOAEL dose in the rat (the most sensitive species) was 30 mg/kg with an average AUC(0-24) and Cmax of 90.5 $\mu\text{g.h/mL}$ and 7.59 $\mu\text{g/mL}$, respectively; the NOAEL dose in the dog was 20 mg/kg with an average AUC(0-24) and Cmax of 147.0 $\mu\text{g.h/mL}$ and 13.3 $\mu\text{g/mL}$, respectively. Due to the presence of heart valvular and vascular lesions in dogs at higher doses, and based on discussions with the GSK Cardiovascular Safety panel, the maximum individual daily human exposure after single or repeat dose in the study will be limited to 4.9 $\mu\text{g.h/mL}$ for AUC(0-24) and 0.443 $\mu\text{g/ml}$ for Cmax (30-fold margins from the dog NOAEL exposures of 147.0 $\mu\text{g.h/mL}$ and 13.3 $\mu\text{g/ml}$, respectively).

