5.6. Trial stopping criteria

The trial will be stopped if either of the following occurs:

- A serious adverse event that is considered to be at least possibly related to GSK3036656 in one or more subjects on active treatment
- Severe, clinically significant non-serious adverse events that are considered to be at least possibly related to GSK3036656 in 2 or more subjects on active treatment in the same group/cohort

If, following an internal safety review, it is appropriate to restart the trial, a substantial amendment will be submitted to the Medicines and Healthcare products Regulatory Agency (MHRA) and Independent Ethics Committee (IEC). The trial will not restart until the amendment has been approved by the MHRA and IEC.

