6.3. Planned Dose Escalation and Adjustments

After the initial dose of GSK3036656, the decision to proceed to each subsequent dose level will be made by the Dose Escalation Committee (DEC) based on safety, tolerability and preliminary pharmacokinetic data from the prior lower dose level (Further details regarding dose escalation can be found in the 201040 Dose Escalation Charter). In Part A, safety data for at least 5 days post-dose and PK data for at least 2 days (48 hours) postdose from at least 4 subjects who received active treatment at the prior lower dose level will be reviewed before dose escalation. In Part B, safety data for at least the first 1 week (7 days) of dosing and PK data for at least the first 2 days (48 hours) of dosing from at least 4 subjects who received active treatment at the prior lower dose level will be reviewed before dose escalation. The actual doses to be administered will be selected by the DEC and may involve either an increase or a decrease in the dose, or repeating the same dose.

The exposures (AUC, Cmax) expected with the next selected dose will be predicted by pharmacokinetic assessment and modelling, and by calculating Bayesian predictive probabilities as data permit (more details in Section 10.3.1).

In toxicology studies in dogs, heart valvular and vascular lesions have been observed at relatively high doses and exposures; no such lesions have been seen in rats at similar exposures. To avoid the risk of this adverse event in the FTIH subjects, exposures in the FTIH study will be limited to predefined levels. Based on discussions with the GSK Cardiovascular Safety panel, the study will aim to limit the maximum individual daily plasma AUC(0-24) and Cmax after single or repeat dose to 4.9 µg.h/mL and 0.443 µg/ml, respectively - a 30-fold margin from the corresponding dog NOAEL exposures of 147.0 µg.h/mL and 13.3 µg/ml at which no valvular or vascular lesions have been detected.

Note: The term “mean” applied to group human exposure parameters (e.g., AUC) in this section refers to Geometric Mean of a dose cohort.

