6.3.1. Dose escalation in Part A

In Part A, bigger dose escalation steps may be allowed at lower doses and systemic exposures as the expected risk of adverse events at these exposures is low. At higher doses, smaller dose escalation steps will be used to minimize the risk of adverse events and gastrointestinal intolerance.

The following rules will guide dose selection in Part A:

1. No dose escalation to the next dose will be higher than 6-fold.
2. Once the dose is ≥ 300 mg, any further dose escalation will be no higher than 3-fold irrespective of the observed exposures.
3. The highest dose in Part A will not exceed 1500 mg.
4. A proposed dose will be acceptable if the predicted probability of an individual exceeding a Day 1 plasma AUC (0-24) of 4.9 µg.h/mL or Cmax of 0.443 µg/mL, as estimated by PK modeling and Bayesian analysis (if feasible), is no more than 10%.

5. Based on prior PK data, individual doses may be adjusted, if needed, such that a predicted individual Day 1 AUC (0-24) or Cmax does not exceed 4.9 $\mu\text{g.h/mL}$ or 0.443 $\mu\text{g/mL}$, respectively.

Dosing with food in Part A will be initiated after the exposures achieved with at least two dose levels administered in a fasted state are already known.

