6.3.2. Dose escalation in Part B

Part B may be initiated after the safety and PK data of at least three doses from Part A are already known. The decision to initiate Part B will be made by the GSK Study team in conjunction with the investigator.

The following rules will guide dose selection in Part B:

1. The starting daily dose in Part B will be selected such that its expected exposure (mean AUC[0-24] or Cmax) on the last day of dosing is no higher than the Day 1 exposure of a dose that has been found to be safe and well tolerated in Part A. The expected daily exposures during the dosing period, including on the last day of dosing, will be predicted based on the PK parameters for GSK3036656 established in Part A. As the highest exposure with repeat dosing is expected on the last day of dosing (as a result of accumulation), this approach would select a daily dose which provides systemic concentrations that, at any time during the period of dosing, are not likely to be higher than the ones already found to be safe and well tolerated in Part A.
2. Subsequent doses in Part B may be selected using the criteria described above for the starting dose in Part B. The expected daily exposures during the dosing period, including on the last day of dosing, will be predicted based on available PK data from Part A and from prior cohorts in Part B. Alternatively, a dose may also be selected even if it does not meet these criteria provided it is no more than 4-fold higher than a previous dose that has been found to be safe and well tolerated upon repeat dosing in Part B.
3. The highest daily dose in Part B will not exceed the highest single dose that has been found to be safe and well tolerated in Part A.
4. A proposed dose will be acceptable if the predicted probability of an individual exceeding a daily plasma AUC (0-24) of 4.9 $\mu\text{g.h/mL}$ or Cmax of 0.443 $\mu\text{g/mL}$ on any day of the dosing period, as estimated by PK modeling and Bayesian analysis (if feasible), is no more than 10%.

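### The individual exposure cap covers repeat dosing, but neither the protocol nor the SAP has an exposure-triggered rule for a Part B subject already on treatment.

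*Protocol*

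**What the plan says.** **The cap.** Protocol 4.5 states that "the maximum individual daily human exposure after single or repeat dose in the study will be limited to" two fixed values: AUC(0-24) of 4.9 µg.h/mL, Cmax of 0.443 µg/mL. Protocol 6.3 is softer, with the same values: "the study will aim to limit the maximum individual daily plasma AUC(0-24) and Cmax after single or repeat dose". The risk table in 4.6.1 gives the reason: heart valve and vascular lesions in dogs, which cannot be monitored in humans.

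**Observed exceedance.** Protocol 5.5 opens "Dose escalation in Part A or Part B will be stopped if any of the following occurs", and item 2 is "At least one subject has a plasma AUC (0-24) higher than 4.9" (in µg.h/mL), with a matching criterion for Cmax, on any day. The Note to 5.5 allows dosing at a lower level. It does not say whether that covers subjects in mid-course.

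**Predicted exceedance.** Under 6.3.2 rule 4 a proposed Part B dose is acceptable if the predicted probability of an individual exceeding either limit "on any day of the dosing period, as estimated by PK modeling and Bayesian analysis (if feasible), is no more than 10" percent. In Part A, 6.3.1 rule 5 adds: "Based on prior PK data, individual doses may be adjusted, if needed". Part B has no counterpart.

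**Stopping rules.** Sections 5.4.1 to 5.4.5 cover liver chemistry, QTc, haematology, vital signs and general safety findings. Section 5.6 ("The trial will be stopped if either of the following occurs") lists adverse events only.

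**Elsewhere.** Protocol 6.3 adds: "Further details regarding dose escalation can be found in the 201040 Dose Escalation Charter". SAP 2.3 describes unblinded PK review at aggregate level, and SAP 7.1.2 calculates exceedance probabilities for candidate future doses.

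**The concern.** When a hazard cannot be watched for in the subject, the exposure limit is the main protection. Section 6.3.2 itself expects exposure to peak on the last dosing day because of accumulation. Every written use of the cap in Part B nevertheless concerns the next dose level. None concerns the person who has already crossed the cap, or whose early data point past it.

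The information exists. Subjects are sampled to 72 h after the Day 1 dose, the sponsor is unblinded, and 5.5 item 2 cannot be applied without looking at individual values. What is missing is the action that follows. At stake is some of the 30-fold margin, for the rest of the course, in a healthy volunteer with no prospect of benefit.

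**Working it through.** **1. The plan's own figure.** Protocol 4.5 sets the caps 30-fold below the dog NOAEL exposures: 147.0/30 = 4.90 µg.h/mL and 13.3/30 = 0.443 µg/mL. Both reproduce.

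**2. Which provision acts on exposure in a Part B subject already on treatment?**

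| Provision | Trigger | Effect |
|---|---|---|
| 5.5 item 2 | Observed AUC or Cmax over the cap | Escalation stops |
| 6.3.2 rule 4 | Predicted probability above 10% | Proposed dose not acceptable |
| 6.3.1 rule 5 | Predicted individual Day 1 exposure | Dose may be adjusted; Part A only |
| 5.4.1 to 5.4.4 | Liver, QTc, haematology, vital signs | Subject stops; no exposure trigger |
| 5.4, 5.4.5 | Investigator judgement, safety findings | Discretionary; exposure not named |
| 5.6 | Adverse events | Trial stops |

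None does.

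**3. How often would it arise?** Part B has 8 active subjects per cohort. With individual risk p and independent subjects, P(at least one over the cap) = 1 − (1 − p)^8:

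- p = 10%: 1 − 0.90^8 = 57%
- p = 5%: 1 − 0.95^8 = 34%
- p = 2%: 1 − 0.98^8 = 15%

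These are ceilings. Shared uncertainty about the PK parameters makes subjects positively correlated, which lowers the chance of at least one.

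**4. How far over, and when?** Assumptions: linear one-compartment PK, once-daily dosing, and lognormal clearance with 50% CV (the value used in 4.5), so log-SD = √ln(1.25) = 0.472. Half-lives are 12, 30 and 72 h (the preclinical average and range in 4.1). The elimination rate k is either fixed or proportional to CL. Cmax is not modelled. AUC on day n is proportional to (1 − exp(−24kn))/CL, with the dose scaled so that P(Day 14 AUC > 4.9) = p, in 1,000,000 simulated subjects. Results among over-cap subjects at p = 10% are given as k fixed / k proportional to CL:

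| Half-life | Median Day 14 AUC | 90th percentile | Over cap on Day 1 | Mean over-cap days from Day 5 | From Day 8 | From Day 11 |
|---|---|---|---|---|---|---|
| 12 h | 5.81 / 5.81 | 8.05 / 8.04 | 29.4% / 0% | 10.0 / 9.8 | 7.0 / 7.0 | 4.0 / 4.0 |
| 30 h | 5.81 / 5.73 | 8.05 / 7.55 | 1.1% / 0% | 9.5 / 7.0 | 6.9 / 6.1 | 4.0 / 3.8 |
| 72 h | 5.81 / 5.43 | 8.05 / 6.40 | 0% / 0% | 6.8 / 3.3 | 5.8 / 3.3 | 3.7 / 2.9 |

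Margins at p = 10%: the median is 147/5.81 = 25.3-fold to 147/5.43 = 27.1-fold, and the 90th percentile is 147/8.05 = 18.3-fold to 147/6.40 = 23.0-fold. At p = 2% the medians run from 5.59 to 5.21, so 26.3- to 28.2-fold.

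**5. What data could drive a rule?** With once-daily dosing, the 24, 48 and 72 h samples after the Day 1 dose are the pre-dose samples of Days 2, 3 and 4. After that the schedule has pre-dose samples on Days 12 and 13 and a full profile on Day 14. A Day 14 exceedance appears after the last dose. An observed-AUC rule can therefore act early only on Day 1, where few exceed, and most of the benefit must come from projection. As a guide, Day 14/Day 1 accumulation is (1 − exp(−14·24k))/(1 − exp(−24k)) = 1.33, 2.35 and 4.66 at 12, 30 and 72 h. The Day 1 AUC that projects to 4.9 is then 4.9/1.33 = 3.68, 4.9/2.35 = 2.09 and 4.9/4.66 = 1.05 µg.h/mL.

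**6. Cost of projection.** Suppose the log-scale prediction error has SD 10% (or 20%) and a subject is flagged when predicted Day 14 AUC exceeds 4.9. At p = 10%, 17–25% (34–47%) of flagged subjects would never have exceeded.

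**The case against.** The protocol's chosen control is dose selection. Under 6.3.2, rule 1 ties the starting dose's expected last-day mean exposure to one already tolerated in Part A, rule 3 sets a ceiling from Part A, and rule 4 openly accepts a residual risk of up to 10%. Section 6.3 says the study aims to limit exposure. The cap is one-thirtieth of a lesion-free exposure from a 4-week dog study, while Part B lasts up to 14 days. Echocardiograms at screening and follow-up, and vital-sign stopping rules for the suspected haemodynamic correlate, add some protection. The investigator may withdraw a subject at any time under 5.4 or adjust a dose under 5.4.5. Extra PK samples are allowed, and the Charter may hold the missing rule.

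Much of this stands, and it is why the expected loss of margin is modest. It does not close the gap. Rule 4 describes a subject before dosing; once that subject's own PK is known, the cohort probability no longer applies. The discretion is optional, lies with a blinded investigator and, in 5.4.5, turns on safety findings that this lesion may not produce. The optional samples carry no dosing action.

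The case against compulsory action on a projection also stands. Early predictions are imprecise, and false flags would cost Day 14 data for a primary PK endpoint.

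**Conclusion.** The concern holds as a gap in the written plan: no exposure-triggered rule applies to a Part B subject already on treatment. The text alone establishes this. The figures show only its size, under the stated assumptions (linear kinetics, 50% CV, preclinical half-lives). Human values will be known by Part B.

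A reader might infer three stronger things that the documents do not support.

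- *That nothing stops a Part B subject.* Sections 5.4.1 to 5.4.4 do, for other reasons.
- *That 57% of cohorts will contain an over-cap subject.* That requires every cohort to sit exactly at the 10% limit with independent subjects.
- *That exceeding the cap means a large loss of margin.* At 30 h, a subject at 80% of the cap on Day 1 would reach 0.80 × 4.9 × 2.348 = 9.2 µg.h/mL on Day 14, about 16-fold. Under the model, only about 0.2–0.45% of subjects get that high, even at the 10% limit.

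Nor can the benefit of early action be taken for granted. Assay turnaround is not given. The escalation review times in 6.3 are minimums, and SAP 2.3.2 allows sequential cohorts, so no review need fall in mid-course. Whether the Charter already covers the point cannot be determined here. This is a cheap improvement that should be made, not a fundamental flaw.

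**What to change.** 1. **Observed exceedance (5.4 and 6.3.2), mandatory.** If a Part B subject's observed AUC(0-24) or Cmax exceeds the cap on any day, that subject's remaining doses are stopped or reduced.
2. **Predicted exceedance (6.3.2), permissive.** Extend 6.3.1 rule 5 to Part B. Once Day 1 to 72 h PK is available, the unblinded sponsor team reviews it by subject. It may reduce or stop remaining doses when a later-day exceedance is predicted at or above a probability fixed in advance. Set a target day for this review that applies whether cohorts overlap or run in sequence, and a way of passing the change to the site that protects the blind as far as possible.
3. **SAP 2.3.** Record this subject-level review as an exception to aggregate-level PK review.
4. **If the Charter already requires this,** cross-reference it in 5.4 and 6.3.2 instead.

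The change uses samples already scheduled and a sponsor already unblinded. Its costs are the possible loss of a flagged subject's full-dose Day 14 profile (including some who would not have exceeded), some risk of unblinding the investigator, and a need for timely assay results even when cohorts run in sequence.
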